1.2. The Problems/Study Rationale

1.2.1. Malnutrition in the ICU

Many critically ill patients develop malnutrition during hospitalization. Malnutrition is a complication which adversely affects clinical outcomes, including length of hospital stay, morbidity, and mortality. The characteristics of ICU patients have changed during the last decade; they now tend to be older and their medical disorders more complex with frequent comorbidities. These factors may contribute to malnutrition in the ICU. Additionally, the combination of stress and undernutrition is associated with negative energy balances and the loss of lean body mass².

Mechanically ventilated patients are unable to take food orally and therefore are dependent on enteral nutrition for provision of both energy and protein requirements. Many critically ill patients often have pre-existing conditions, including malnutrition. All of this predisposes patients to nutrition deficits, muscle wasting, delayed wound healing, slower recovery, and increased risk of morbidity and mortality. There is a consensus that supplemental nutrition support is needed and improves outcomes for patients³.

Providing adequate energy via nutrition support to the mechanically ventilated patient is critical. In the mechanically ventilated patient, overfeeding, even for short periods of time, can lead to hyperglycemia and increases time on the ventilator. Conversely, an increasing caloric deficit (persistent underfeeding) also increases time on the ventilator. Providing early nutritional intervention may shorten hospital stays by 2 days, lower readmission rates by 27% and save \$3,800 per patient.

Indirect calorimetry is the recommended method for determining patients' resting energy expenditure (REE). A 2015 estimate showed that only 2% of ICUs were regularly using indirect calorimetry. Predictive equations have therefore been the most commonly practiced method of determining energy needs; however, the literature clearly indicates that each equation has a large potential for error. This makes it difficult to accurately predict an individual patient's energy requirements during critical illness. In general, predictive equations estimate accurately only 50% of the time in ICU patients⁴.

² Thibault R, Pichard C. Nutrition and clinical outcome in intensive care patients. Curr Opin Clin Nutr Metab Care 2010; 13(2):177-83

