³ Allen, K., Hoffman, L. Enteral Nutrition in the Mechanically Ventilated Patient. Nutr in Clin Pract. Vol 00 2009/1-18. DOI: 10.1002/ncp.10242.

⁴ Allen, K., Hoffman, L. Enteral Nutrition in the Mechanically Ventilated Patient. Nutr in Clin Pract. Vol 00 2009/1-18. DOI: 10.1002/ncp.10242.

Subject: smART Plus Comparative Study Protocol - Beilinson

The American Association for Parenteral and Enteral Nutrition recommends that for patients who are at high risk for malnutrition, efforts should be made to provide >80% of the estimated or calculated energy and protein goal within 48–72 hours, starting with half the patient's calorie goal with the rate slowly increasing over time, in order to achieve the clinical benefit of enteral nutrition over the first week of hospitalization⁵. However, studies have shown that more than 74% of ICU patients failed to receive at least 80% of their proscribed nutrition⁶. Gastric retention and intolerance are usually measured by means of extraction and assessment of the gastric residual volume (GRV). However, the nutrients lost through GRV assessments are often not compensated for. In addition, feeding is regularly paused for medical intervention and imaging occurring outside of the unit.

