1.8.2. Known potential benefits

Subject: smART Plus Comparative Study Protocol - Beilinson

As explained above, the various components of the smART+ System must operate as a cohesive system in order to allow feeding optimization as demonstrated in the flowchart below. With validation of the smART+ features during the study, the clinical benefit of the device will be the lowering of risks associated with tube displacement and malpositioning as well as lowering the risks associated with reflux and aspiration.

In addition, the smART+ System is able to continuously measure the patients REE and minimize the risk of overfeeding. Therefore, by reducing overfeeding it not only achieves feeding optimization, but it also reduces the likelihood of reflux episodes due to overfeeding.

2. Objectives and Endpoints

2.1. Primary Endpoint:

 ART MEDICAL PATIENT SAFETY TECHNOLOGY	Number: CRO-C-2822	Date issued: 01-Mar-2021
	Rev.06	Page 15 of 35

Subject: smART Plus Comparative Study Protocol - Beilinson

Optimization of the delivery of nutrition by the smART+ System as compared to standard of care, by automatically calculating and administering enteral feeding better than standard of care (REE or Calorimeter).

Optimization is defined as the ability of the system to provide adequate nutrition (not overfeed or underfeed) when compared to treatment via standard of care.

Evaluation will be conducted based on an analysis and comparison of the following parameters (obtained through the hospital's electronic records for control group and smART+ records for the treated group):

- Patient caloric target set
- Volume of patient nutritional intake value versus actual patient need – this is calculated by assessing the actual nutrition delivered, discarded nutrition in the GRV bags as well as the unused quantity in discarded feed bottles (if applicable).

As part of optimization evaluation, feeding efficiency calculation ((Net nutrition delivered [ml])/ (VTBD [ml])) should be calculated for the days when the patient received enteral feeding that given under medical order, removed from the patient, or stopped feeding that was not renewed until the end of the study. Feeding efficiency should not be calculated for the days that patient has been discontinued from enteral feeding by a medical order.

2.2. Secondary Endpoints:

- Safety

Safe use of the entire system will be assessed based on the occurrence of device related AE or SAE.

- Decrease in ICU length of stay.

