9.1 Sample size consideration

Approximately 200 subjects will be enrolled for the complete multi-center comparative study (100 per group). An interim analysis will be performed after 100 subjects (50 in each group) are enrolled on the primary endpoint.

1- Based on the primary endpoint at interim analysis (feeding efficiency):

Sample size rationale:

The rationale for sample size calculation is based on a difference in feeding efficiency between the tested group (with smART+ System) and the current standard practice (group B).

Sample size justification:

The comparison between groups of food consumption estimations is reflected by Effect size, calculated as the difference between the groups normalized by the common standard deviation.

The calculation uses the following formulation: (Estimation in the tested group - Estimation in control group)/Common standard deviation Error! Bookmark not defined.Error! Bookmark not defined.

A sample size of 50 in each group will have 90% power to detect an **effect size of 0.70** using a two-group t-test with a 0.025 two-sided significance level. [1, 2]

A significance of 0.025 was used instead of the usual 0.05 (alpha adjustment) due to the increase in the chance of making a Type 1 error following two subsequent analysis.

2- Based on the secondary endpoints at end of study:

2.1 Ventilation days:

Sample size rationale:

Subject: smART Plus Comparative Study Protocol - Beilinson

The rationale for sample size calculation is based on a difference in Ventilation days between the tested group (with smART+ System) and the current standard practice (group B).

Sample size justification:

The comparison between groups in ventilation days is reflected by Effect size.

A sample size of 100 in each group will have 90% power to detect an **effect size of 0.46** using a two group t-test with a 0.05 two-sided significance level. [1, 2]

2.2 Ventilation Associated Events:
Sample size rationale:

The rationale for sample size calculation is based on a difference in the proportion of subjects with Ventilation-Associated Events between the tested group (with smART+ System) and the current standard practice (group B) of 20%.

Sample size justification:

A two group continuity corrected c^2 test with a 0.05 two-sided significance level will have 90% power to detect the difference between a Group 1 proportion, p_1 , and a Group 2 proportion, p_2 (**odds ratio of 2.70**) when the sample size in each group is 100.[3]

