2.3 Length of stay:
Sample size rationale:

The rationale for sample size calculation is based on a difference in length of stay between the tested group (with smART+ System) and the current standard practice (group B).

Sample size justification:

The comparison between groups in ventilation days is reflected by Effect size.

A sample size of 100 in each group will have 90% power to detect an **effect size of 0.46** using a two group t-test with a 0.05 two-sided significance level. [1, 2]

References:

9.2 Endpoints analysis:
9.2.1 General:

All measured variables and derived parameters will be listed individually and, if appropriate, tabulated by descriptive statistics.

 ART MEDICAL PATIENT SAFETY TECHNOLOGY	Number: CRO-C-2822	Date issued: 01-Mar-2021
	Rev.06	Page 31 of 35

Subject: smART Plus Comparative Study Protocol - Beilinson

For categorical variables summary tables will be provided giving sample size, absolute and relative frequency and 95% CI (Confidence Interval) for proportions by study arm.

For continuous variables summary tables will be provided giving sample size, arithmetic mean, standard deviation, coefficient of variation (CV%), median, minimum and maximum and 95% CI (Confidence Interval) for means of variables by study arm.

All tests will be two-tailed, and a p value of 5% or less will be considered statistically significant.

The data will be analyzed using the SAS® version 9.4 (SAS Institute, Cary North Carolina).

9.2.2 Primary endpoint:

The two-sample T-test or Non-parametric Wilcoxon-Mann-Whitney Rank sum test for independent samples (as is appropriate) will be applied for testing the statistical significance of the difference in feeding efficiency between the study groups.

9.2.3 Secondary endpoints:

- The two-sample T-test or Non-parametric Wilcoxon-Mann-Whitney Rank sum test for independent samples (as is appropriate) will be applied for testing the statistical significance of the difference in number of ventilation days (Evaluated by the number of hours of etCO2 from the hospital electronic records) between the study groups.

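### The only primary test, a plain difference in feeding efficiency, does not by itself establish optimization as section 2.1 defines it

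*Combined protocol and SAP*

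**What the plan says.** Section 2.1 states the primary endpoint as the system "automatically calculating and administering enteral feeding better than standard of care". It then gives the meaning: "Optimization is defined as the ability of the system to provide adequate nutrition (not overfeed or underfeed"). Evaluation is to rest on an analysis and comparison of two listed parameters: the caloric target, and "Volume of patient nutritional intake value versus actual patient need". Feeding efficiency, net nutrition delivered (ml) over VTBD (ml), comes in as one part of that evaluation. VTBD is not spelled out in the text or in the list of abbreviations.

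Section 9.2.2 names one primary analysis, a t-test or Wilcoxon-Mann-Whitney test for "testing the statistical significance of the difference in feeding efficiency between the study groups". Section 9.1 sizes the trial on the same variable, with the signed effect size "Estimation in the tested group - Estimation in control group)/Common standard deviation" set at 0.70, 50 per group and two-sided 0.025.

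For everything else, section 9.2.1 says: "All measured variables and derived parameters will be listed individually and, if appropriate, tabulated by descriptive statistics". It goes on to provide summary tables for continuous variables by arm, with a 95% CI for each mean.

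**The concern.** The endpoint is about closeness to need, with failure possible on either side. The test is about which arm has the larger ratio. These agree only when programmes are set close to need and delivery falls short of it.

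The plan's own rationale makes both directions matter. Section 1.2.1 says that "overfeeding, even for short periods of time, can lead to hyperglycemia and increases time on the ventilator", and that a growing caloric deficit also prolongs ventilation. Section 1.8.2 claims less overfeeding as a benefit of the device. Section 1.7 says the system makes up for lost feeding time and discarded content, which raises the numerator of the ratio.

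At stake is what a significant result may be said to show. A reader of 2.1 would take it as evidence of better calculation and adequate feeding, and the test speaks to neither. Section 7.1 also lists meeting the primary endpoint among the reasons for ending the study, so the conclusion could rest on the interim data from 50 per group.

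**Working it through.** **The plan's own figure.** Power with n = 50 per group, effect size 0.70 and two-sided 0.025: Φ(0.70·√(50/2) − 2.241) = Φ(1.259) = 0.896. The exact t-test gives 0.888. The stated 90% reproduces, so the sample size arithmetic is not at fault.

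**What the ratio measures.** Let k be programme/need.
- *VTBD = programmed volume.* Feeding efficiency is delivered/programme, while intake/need is efficiency × k. The test never sees k. A programme set wrong leaves the tested difference and its power unchanged.
- *VTBD = volume needed.* The ratio is intake/need, but the signed difference rewards a rise from 1.00 to 1.10 as much as one from 0.80 to 0.90.
- *A pump that stops at VTBD.* The gross volume cannot exceed VTBD, so the ratio cannot show overfeeding at all.

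**Illustration (hypothetical).** The measure is the mean per-patient |intake/need − 1|. For normal data with mean μ, SD s and d = μ − 1:

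E|X − 1| = s·√(2/π)·exp(−d²/2s²) + d·[1 − 2Φ(−d/s)]

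Assumptions: a difference of 0.10 at the plan's effect size of 0.70, so s = 0.10/0.70 = 0.143; efficiency 0.95 in A and 0.85 in B; B programmed at need; VTBD = programme.
- B: d = −0.15, giving 0.066 + 0.106 = 0.172.
- A with k = 1: d = −0.05, giving 0.107 + 0.014 = 0.121, so A is nearer.
- A with general k (mean 0.95k, SD 0.143k): equal to B's 0.172 at k = 0.885 and k = 1.187. Outside those limits A is further from need than B, yet the test still has about 90% power to favour A.

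**Varying the SD.** The effect size is held at 0.70, so s = difference/0.70:

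| A v B efficiency | SD | B's distance | A's distance, k = 1 | A nearer need if k is within |
|---|---|---|---|---|
| 0.95 v 0.90 | 0.071 | 0.105 | 0.070 | 0.946 to 1.153 |
| 0.95 v 0.85 | 0.143 | 0.172 | 0.121 | 0.885 to 1.187 |
| 0.94 v 0.80 | 0.200 | 0.233 | 0.167 | 0.831 to 1.228 |
| 0.95 v 0.75 | 0.286 | 0.310 | 0.231 | 0.743 to 1.226 |

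The lower limit therefore runs from about 0.74 to 0.95. No single threshold is robust.

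**Using the plan's background figure.** Section 1.2.1 reports that "more than 74% of ICU patients failed to receive at least 80% of their proscribed nutrition". If B followed it with SD 0.143, its mean would be 0.80 − 0.643 × 0.143 = 0.708, and A's 0.808. The limits become 0.875 and 1.570. Overfeeding by A would have to be extreme to reverse the ranking; a programme about 12% below need would be enough on the other side.

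**VTBD = need, same SD (hypothetical).** At 1.05 v 0.95 both arms are 0.121 away. At 1.10 v 1.00, A is 0.141 away and B 0.114. Both are differences of 0.10 in A's favour under the planned test.

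**The opposite miss.** In 20,000 simulated trials with 50 per group and both means at 1.00, but SD 0.10 in A and 0.30 in B, A is truly closer to need. The planned test favours A in 1.3% of trials, which is chance. A t-test on |ratio − 1| favours A in about 100%.

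**The case against.** Need is not absent from the plan. Section 2.1 commits to comparing target and intake with need, and calls feeding efficiency only a part of the evaluation. Section 9.2.1 provides tables by arm with 95% CIs; the words about appropriateness qualify tabulation, not listing. A reader might infer that the trial ignores need, or that a shortfall could surface only in optional tables. The documents do not support that. What is missing is a named between-group comparison and a stated reference for need.

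A reader might also infer that the device is likely to overfeed and be credited for it. That is not supported either. Section 9.2.2 is two-tailed and states no direction; that more counts as better follows from the signed effect size and the superiority aim. The numerator is net of discarded volume, and the only background figure shows under-delivery. Where delivery is mostly below target, a reversal through overfeeding is remote.

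Higher efficiency does mean intake closer to need when programmes sit near need. All means and SDs above are assumed, and nothing in the documents shows that group A's programmes will be far from need.

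Finally, a comparison that takes need from each arm's own method cannot show that the console's REE is right. If that REE is wrong and staff programme to it, A still looks better (0.121 v 0.172 in the main example). This stands, and limits what the added analysis may claim. It would still show over- and underfeeding against recorded need, which the planned test does not.

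**Conclusion.** The concern holds in a limited form. A significant difference in feeding efficiency does not by itself establish optimization as 2.1 defines it, under either reading of VTBD. This follows from the wording of 2.1, 9.1 and 9.2.2 and needs no numerical assumption.

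The size is conditional. With 0.95 v 0.85, SD 0.143, normal data and B programmed at need, the planned test and closeness to need agree while A's programme is about 0.89 to 1.19 of need. The lower limit moves between roughly 0.74 and 0.95 with the SD. Underfeeding relative to need is the more plausible way for them to disagree. The examples are not predictions, and do not show that the device calculates need badly. The change should be made, and before the interim analysis so that it remains prespecified.

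**What to change.** 1. In 2.1, define VTBD. Limit the conclusion from the feeding-efficiency test to delivery of that volume, with no claim of better calculation or adequacy from that test alone.
2. In 9.2.2, add a supportive between-group comparison of the per-patient mean of |net intake/recorded need − 1| over the feeding days that 2.1 defines, with a 95% CI for the difference. Summarise signed intake/need and target/need by arm.
3. State that recorded need comes from different methods: console REE in group A (5.2.5), and REE, calorimeter or another method in group B (5.3.2, 5.3.3). The comparison therefore measures adequacy against recorded need and validates neither estimate. The schedule of activities repeats REE only in group A, so repeat the analysis with baseline need in both arms.
4. Add a sensitivity table rescaling each arm's need in turn by 0.85, 0.90, 1.10 and 1.15, and report where the ranking reverses. In the 0.95 v 0.85 example it reverses only when A's need is multiplied by 1.15: the mean becomes 0.95/1.15 = 0.826, the SD 0.143/1.15 = 0.124, and the distance 0.183 against 0.172.

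The cost is wording in 2.1, one extra analysis and one table. Food types, amounts, discarded residuals, console REE and group B's calorimeter and nutrition data are already collected (5.2.8, 5.3.5). As the comparison is supportive, the sample size need not change. It will be less sensitive than the primary test: in the simulated case of 0.94 v 0.80 with SD 0.20 and 50 per group at 0.025, it favours A in 52.1% of trials, against 88.9% for the raw ratio. The other downsides are a narrower primary claim and an imperfect reference for need.

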5.2.3. Feeding insertion- group A

Study staff should follow the device instructions for use and specific instructions provided by the console during initial tube placement. Time of tube placement is recorded by the console. Once initial placement is confirmed by the system, verification of correct placement should

 ART MEDICAL PATIENT SAFETY TECHNOLOGY	Number: CRO-C-2822	Date issued: 01-Mar-2021
	Rev.06	Page 19 of 35

Subject: smART Plus Comparative Study Protocol - Beilinson

be performed according to hospital procedures (such as abdominal /chest X-ray /other gold standard).

5.2.4.Vital signs- group A

Vital signs (e.g., temperature, pulse, respirations, blood pressure) should be noted within 10 minutes of feeding tube insertion.

5.2.5.REE measurement- group A

Once the patient has recovered from the process of inserting the feeding tube, a baseline REE measurement should be taken using the smART+ flow sensor and CO₂ sensor.

5.2.6.Feeding program- group A

Once the REE measurement is accomplished, personnel authorized by the hospital should program a suitable feeding program using the smART+ Console and in accordance with hospital procedure.

5.2.7.Ongoing use- group A

If system alerts of tube displacement during ongoing use, the need for tube reinsertion/repositioning should be evaluated and performed as needed.

If system alerts an increase in REE, the message should be evaluated by personnel authorized by the hospital, who should decide if to change the patient's feeding program.

5.2.8.Data recording- group A

The following information will be acquired from the patient's medical chart (recorded in the hospital sources) into the eCRF, for each patient

- Initial screening: as detailed in the study eCRF
- Feeding information: Food types, amounts, rate, water delivery, parenteral nutrition, TPN, other nutritional data
- Gastric residual volume: discard gastric residuals amount, GRV procedure times.
- Medications provided: as detailed in the study eCRF.
- Lab results: patient lab results, as detailed in the study eCRF, and obtained 24 hours prior the feeding tube insertion and during the study, should be recorded in the eCRF.
- Imaging: (X-ray, CT, and alike) performed during the study should be obtained and attached to the eCRF.
- Urine: amounts, rates, times, warnings
- ICU submission and discharge ordering times
- Breathing data reports starting from the ICU admission (FiO₂, PEEP)
- Demographics

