The following information will be recorded by the smART+ console (or accompanying recording equipment) and extracted directly by the sponsor:

 ART MEDICAL PATIENT SAFETY TECHNOLOGY	Number: CRO-C-2822	Date issued: 01-Mar-2021
	Rev.06	Page 20 of 35

Subject: smART Plus Comparative Study Protocol - Beilinson

- Urine monitoring: amounts, rates, times, warnings, trends (and all other data collected by the smART+ System).
- Feeding information: Food types, amounts, rate, fluids delivery (and all other data collected by the smART+ System).
- Gastric residual volume: GRV amounts and times
- Reflux and position data
- REE data
- Breathing data (collected by the smART+ System)
- All other data collected by the smART+ System.

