5.3. Group B- Control Group

5.3.1. Nutrition camera - group B

Local site procedure for changing feeding bottle/bag should be followed as needed and according to hospital procedures. An additional camera (Nutrition camera) will be added, pointed directly at the feeding bottle/bag area and not on the patient.

The Nutrition camera will record a real time video and automatically save it in storage device (such as PC). This camera captures the amount of feeding discarded that was not used for patient feeding. It will allow later data analyzation to quantify the amount of feeding discarded by using the grid lines marked on the feeding bag's/bottle's exterior. In order to ensure the effectiveness of the Nutrition camera, it will bear an instruction such as Ensure camera points at feeding bottle/bag.

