5.3.5. Data recording- group B

The following information will be acquired from the patient's medical chart (recorded in the hospital sources) for each patient:

- Initial screening: as detailed in the study eCRF
- Feeding information: Food types, amounts, rate, water delivery, parenteral nutrition, TPN, Indirect calorimeter and other nutritional data.
- Gastric residual volume: discard gastric residuals amount, GRV procedure times.
- Medications provided: as detailed in the study eCRF.
- Lab results: all patient lab results ordered during the study as well as all available lab results obtained 24 hours prior to study enrollment and added to the eCRF.
- Imaging: patient imaging (X-rays, CT, and alike) performed during the study should be obtained and added to the eCRF.
- Urine monitoring: amounts, rates, times, warnings and all data related to urinary output and diagnosis, and found in the hospital source.
- ICU submission and discharge ordering times
- Breathing data reports starting from the ICU admission (FiO2, PEEP)
- Demographics

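### Feeding efficiency is measured by a different method in each arm, and the primary analysis has no check that could tell a recording difference from a treatment effect

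*Combined protocol and SAP*

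**What the plan says.** Section 2.1 lists two parameters for judging optimization: the caloric target, and nutritional intake against need. It says they come from "electronic records for control group and smART+ records for the treated group". Intake is worked out by "assessing the actual nutrition delivered, discarded nutrition in the GRV bags as well as the unused quantity in discarded feed bottles (if applicable"). The next paragraph makes feeding efficiency, net nutrition delivered divided by VTBD (both in ml), part of that evaluation. VTBD is not defined there or in the list of abbreviations. Section 9.2.2 tests feeding efficiency between groups with a two-sample t-test or a Wilcoxon-Mann-Whitney test.

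The data-recording sections add detail:

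- **Group A, console (5.2.8).** Feeding and GRV data, among others, "will be recorded by the smART+ console (or accompanying recording equipment) and extracted directly by the sponsor".
- **Group A, chart (5.2.8).** The same section opens: "The following information will be acquired from the patient's medical chart (recorded in the hospital sources) into the eCRF, for each patient". The items include "Feeding information: Food types, amounts, rate, water delivery, parenteral nutrition, TPN, other nutritional data" and the discarded gastric residual amount.
- **Group B, chart (5.3.5).** The list again has feeding types, amounts and rate, and "Gastric residual volume: discard gastric residuals amount, GRV procedure times".
- **Group B, camera (5.3.1).** A Nutrition camera points at the feeding bag or bottle: "This camera captures the amount of feeding discarded that was not used for patient feeding". No feed-bag camera is described for group A. Its camera is near the patient's head and optional (5.2.1).

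The trial is open label (5.1).

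**The concern.** Randomization balances the patients. It does not balance a measurement step that comes after allocation and differs by arm. If the console and the chart would give different volumes for the same patient on the same day, that gap enters the between-arm difference in full, and a larger sample only makes it easier to detect as if it were an effect.

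The plan has nothing that would reveal such a gap. It describes no comparison of console and chart volumes, no blinded reading of the camera or chart, and no analysis with both arms measured from one source. The group A video is to be compared with the console logs, but what it records is tube movement and medical procedures, not feed volume. At stake is whether a significant difference in feeding efficiency, in either direction, can be attributed to the device.

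**Working it through.** **Inputs from the documents (9.1).** 50 per group at the interim analysis, standardised effect 0.70, two-sided alpha 0.025, power 90%, two-group t-test. The final size is 100 per group. Section 9.2.1 calls a p value of 5% or less significant, so the final analysis is shown at both levels.

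**Assumed inputs.** The documents give no standard deviation (SD) for feeding efficiency; 0.15 to 0.20 is assumed. The offsets of 1, 3 and 5 efficiency points are also assumed. For scale, the feed rate of about 50 cc/hr in 1.1.2 is 50 × 24 = 1200 ml/day. If that stood for VTBD, 5 points would be 0.05 × 1200 = 60 ml/day.

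**Reproducing the plan's figure.** The normal approximation with effect 0.70, alpha 0.025 and 90% power needs 51 per group. At 50 per group it gives 89.6% power, and the noncentral t gives 88.8%. The stated 50 per group and 90% are reproduced within rounding.

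**Offset with no true effect.** Let b = offset / SD. The test statistic is noncentral t with 2n − 2 degrees of freedom and noncentrality b × √(n/2). At n = 50, √(n/2) = 5 and the critical value is 2.276. The table gives the two-sided rejection probability.

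| Offset (points) | SD | b | Noncentrality, n = 50 | 50/group, α 0.025 | 100/group, α 0.025 | 100/group, α 0.05 |
|---|---|---|---|---|---|---|
| 0 | any | 0 | 0 | 2.5% | 2.5% | 5.0% |
| 1 | 0.20 | 0.05 | 0.25 | 3.0% | 3.4% | 6.4% |
| 1 | 0.15 | 0.067 | 0.33 | 3.3% | 4.1% | 7.6% |
| 3 | 0.20 | 0.15 | 0.75 | 6.8% | 11.8% | 18.4% |
| 3 | 0.15 | 0.20 | 1.00 | 10.6% | 20.2% | 29.1% |
| 5 | 0.20 | 0.25 | 1.25 | 15.7% | 31.4% | 42.1% |
| 5 | 0.15 | 0.333 | 1.67 | 27.6% | 54.0% | 65.0% |

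At 3 and 5 points nearly all of these rejections fall on the side the offset favours.

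**Offset against the device.** With a true effect of 0.70 SD and an offset of b SD the other way, the test sees 0.70 − b. At 50 per group and alpha 0.025, power falls from 88.8% to 76.4% at b = 0.1 and to 59.0% at b = 0.2.

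**Direction.** The documents do not settle it. Discarded GRV missing from control charts would make control efficiency look too high. Delivered feed missing from control charts would make it look too low.

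**The case against.** The strongest objection is that a same-source analysis may not remove the confounding. In group A the console pump delivers the feed and the hub controls GRV release, so charted volumes may simply be copied from the device. The documents do not say. If they are copied, the console-minus-chart difference would be near zero by construction, and chart against chart would still be device readings against manual entries. This stands as a limit on what the remedy can show. It is not a reason to leave the arms uncompared on a common basis.

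Several stronger readings are tempting, and the documents do not support them:

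- *The primary result will be biased toward the device.* No offset is shown to exist, its direction is unknown, and at 1 point its effect is close to nominal.
- *Both numerator and denominator come from the console in group A.* The source statement in 2.1 is attached to the two listed parameters. Feeding efficiency follows in its own paragraph with no source given, and VTBD is undefined. A different source for the denominator is an inference.
- *Subtracting unused bottle feed only in group B is itself a bias, so it should be done in both arms or in neither.* If control charts record volume hung while the console records volume pumped, the camera correction may be what makes the arms comparable. Subtracting bottle remains from a pumped volume would remove feed that was never counted. Unused bottle volume is not a listed data item for group A, and 2.1 already says the subtraction applies where applicable.
- *Superiority should require the chart analysis to agree.* That rule has no natural criterion and costs power. If chart reliability were 0.8 (an assumption), the effect would shrink to 0.70 × √0.8 = 0.63, and power at 50 per group would fall from 89% to 80% before any joint requirement. In an open-label trial, manual charting is also not clearly less open to bias than an automatic log.

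**Conclusion.** The point holds as a gap in the analysis plan. For the parameters behind the primary endpoint, measurement method is confounded with arm, and the test in 9.2.2 cannot distinguish a recording difference from a treatment effect. How much this matters is conditional. The figures rest on an assumed SD of 0.15 to 0.20 and assumed offsets: at the interim analysis, false-positive rates of about 3% for 1 point, 7 to 11% for 3 points and 16 to 28% for 5 points, against a nominal 2.5%. The same offset does more damage at 100 per group, and an offset against the device costs power. A reader might infer that the trial is known to favour the device; the documents do not go that far. What they support is that an offset in either direction would go unseen under the current plan, although group A chart data that could help to expose it are already being collected.

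**What to change.** Keep the planned primary analysis and make these changes:

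1. In 9.2.2, prespecify a sensitivity analysis that computes feeding efficiency in both arms from the hospital-chart feeding and discarded-GRV data already collected under 5.2.8 and 5.3.5.
2. Report the console-minus-chart difference in group A, and state whether the chart values were entered independently of the console.
3. In 2.1, define VTBD and its source identically in both arms.
4. Define net delivered volume as one quantity in both arms: volume reaching the patient minus discarded GRV. Subtract unused bottle volume only where the recorded figure is volume hung and not volume pumped.
5. State that a material difference between the two analyses will be reported as a limit on the superiority conclusion. The chart analysis is not a formal gate.

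The cost is some extra analysis and two definitions. It needs no new patient procedures and no change in sample size. Neither chart list names VTBD or ordered volume, so the team must confirm that the chosen denominator can be obtained in both arms. The downside is that chart values are noisier than logs and may not be fully independent of the console, so agreement between the two analyses would reassure without being conclusive.
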